5.12 Analysis of safety outcomes

For the safety endpoints, all patients that were randomized and received at least 1 dose of the investigated drug or placebo will be included. For the safety analysis, patients will be grouped based on the actual study treatment received.

The safety outcomes are all binary outcomes. For descriptive purposes, the number (%) of failure and success for each safety outcome will be given per treatment arm.

For each safety outcome, the treatment effect will be evaluated by means of a generalized linear mixed model (logistic model). The statistical model will include a fixed treatment effect, and a random centre effect. The results of this model will be presented as an odds-ratio (OR), 95% confidence interval and the associated p value.

7 APPENDIX A – BASELINE CHARACTERISTICS

7.1 Patient characteristics and baseline comparisons

This includes following variables:

Baseline Characteristic	Variable	Type of variable	Overall population (n=x)	High-dose loop diuretics + 500 mg acetazolamide (IV) (n=x)	High-dose loop diuretics + placebo (IV) (n=x)
Age (years)	DEM_AGE	Continue			
Female sex (N,%)	DEM_SEX	Binary			
Caucasian (N,%)	DEM_RACE	Binary			
LVEF (N,%) LVEF ≤ 40% (N,%) LVEF > 40%	MH_LVEFRES	Continue Maar in tabel nadien binair			
Etiology of HF Ischemic (N,%) CABG (N, %) PTCA (N, %) Thrombolysis (N, %) Non-ichemic (N,%) Valvular (N, %) Idiopathic (N,%) Hypertensive (N,%) Toxic (N,%)	MH_HFOPT, MH_HF_ISOPT, MH_HF_NISOPT	Nominal			
NYHA class at enrolment Class II (N,%) Class III (N,%) Class IV (N,%)	MH_NYHAOPT	Ordinal			
Comorbid conditions Atrial fibrillation or atrial flutter (N,%) Stroke (N,%) Diabetes (N,%) Hypertension (N,%) Valve surgery (N,%) PAD (N,%) COPD (N,%)	MH_AFYN, MH_STROKEYN, MH_DIABYN, MH_HYPERTOPT , MH_VALVESURY N, MH_PADYN, MH_COPDYN	Nominal			
CRT/ICD at enrolment None (N,%) pacemaker – single chamber (N,%) pacemaker-dual chamber (N,%) ICD-primary prevention (N,%) ICD-secondary prevention (N,%) CRT-D (N,%) CRT-P (N,%)	MH_CADOPT,	Nominal			
Smoking status at enrolment Never (N,%)	MH_SMOKEOPT	Nominal			

Baseline Characteristic	Variable	Type of variable	Overall population (n=x)	High-dose loop diuretics + 500 mg acetazolamide (IV) (n=x)	High-dose loop diuretics + placebo (IV) (n=x)
Former (N,%) Current (N,%)					
Malignancy requiring chemo/radiotherapy No (N,%) Yes-past (N,%) Yes-current (N,%) Yes-past and current (N,%)	MH_TUMORYN	Nominal			
Weight (kg)	VS_WGHT_D0	Continue			
Pulse (beats/min)	VS_PULSE_D0	Continue			
Blood pressure (systolic) (mmHg)	VS_BPS_D0	Continue			
Blood pressure (diastolic) (mmHg)	VS_BPD_D0	Continue			
Mean Arterial Pressure (MAP)	VS_MAP_D0	Continue			
Congestion score	VOA_SCORE_D0	Ordinal			
Laboratory values Hematology (g/dL) Hematocrit (%) Sodium (mmol/L) Potassium (mmol/L) Chloride (mmol/L) Serum osmolality (mOsm/kg) Serum urea (mg/dL) eGFR (mL/min/1,73m²) Total protein (g/L) Albumin (g/L) Fe (µg/dL) Ferritin (µg/dL) Transferrin saturation (TSAT) (%) LDH (U/L) Troponin (ng/L) NTproBNP/BNP	LABB_HGB_D0, LABB_HT_D0, LABB_NA_D0, LABB_K_D0, LABB_CL_D0, LABB_OSM_D0, LABB_UREA_D0, LABB_GFR_D0, LABB_PROT_D0, LABB_ALB_D0, LABB_FE_D0, LABB_FERR_D0, LABB_TSAT_D0, LABB_LDH_D0, LABB_TROP_D0, LABB_BNPOPT_D0, LABB_BNP_D0	Continue			
Diuretics Furosemide (mg) Thiazide (N,%) MRA (N,%)	Report parent 'Screening': DIU_TYPE + DIU DOSIS Report parent 'Screening': DIU_TYPE	Continue Nominal			
Neurohumoral blockers ACE (N,%) Beta-blocker (N,%) ARB (N,%) Entresto (N,%)	Report parent 'Screening': NH_TYPE	Nominal			
Other concomitant medication Ivabradine (N,%) Hydralazine (N,%)	CONMED_OTHE R_D0	Nominal			

Baseline Characteristic	Variable	Type of variable	Overall population (n=x)	High-dose loop diuretics + 500 mg acetazolamide (IV) (n=x)	High-dose loop diuretics + placebo (IV) (n=x)
Molsidomine (N,%) Isosorbide dinitrate, PO (N,%) Digoxin (N,%) Aspirin(N,%) NOAC/DOAC VKA (N,%) P2Y12 (N,%) Statin (N,%) XO-inhibitor (N,%) Amiodarone (N,%) Flecainide (N,%) IV inotropes (N,%) IV vasodilators (N,%) Other anti-hypertensive drugs (N,%) Iron, PO (N,%) Iron, IV (N,%) SGLT2-i (N,%) None (N,%)					
EQ-5D-5L (N, %) EQ-5D-5L score	EQ5D_D0 Report parent 'Screening': EQ5D_MOBOPT, EQ5D_SCOPT, EQ5D_ACTOPT, EQ5D_PAINOPT, EQ5D_ANXOPT	Nominal Continue			
EQ-5D-5L (VAS) (N,%) (0-100)	EQ5D_SCORESL	Continue			

1 DOCUMENT HISTORY

Version number	Version Date	Author	Reason for change
Version 1.0	17 January 2022	ADVOR Scientific Study Team [REDACTED] (Statistician)	First version
Version 2.0	17 March 2022	ADVOR Scientific Study Team [REDACTED] (Statistician)	Appendix A Baseline Characteristics: The Baseline Characteristics Iron PO and Iron IV mentioned in the Appendix A have been removed because these data will not be collected during the study.

3 LIST OF ABBREVIATIONS

The following table presents the abbreviations and acronyms used in the Statistical Analysis Plan:

CI	Confidence Interval
EAC	Endpoint Adjudication Committee
eCRF	electronic Case Report Form
eGFR	Estimated glomerular filtration rate
EMA	European Medicines Agency
EQ-5D	EuroQol five dimension (questionnaire)
HF	Heart Failure
HFpEF	Heart Failure with preserved Ejection Fraction
HFrEF	Heart Failure with reduced Ejection Fraction
HR	Hazard Ratio
IMP	Investigational Medicinal Product
IRT	Interactive Response Technology
ITT	Intention To Treat
ITTAS	Intention to treat analysis set
IV	Intravenous
KCl	Potassium chlorate
LVEF	Left Ventricular Ejection Fraction
MgSo ₄	Magnesium sulfate
NaHCO ₃	Sodium bicarbonate
OR	Odds ratio
QoL	Quality of Life
SAS	Statistical Analysis System
SD	Source Documents
SGLT2-i	Sodium-glucose Cotransport 2 Inhibitor
SOC	Standard Of Care
SUSAR	Suspected Unexpected Serious Adverse Reactions

4 STUDY SYNOPSIS

The ADVOR study is a phase IV randomized, multicentre, double-blind study, comparing monotherapy with high-dose loop diuretics (standard of care - SOC) versus combination therapy with acetazolamide and high-dose loop diuretics in patients with decompensated heart failure (HF) and clinical signs of volume overload. For more details regarding the intervention see section 4.3

The study consists of 3 phases:

- **screening phase:** starting from identifying a study subject prior to / during hospitalization until the first dose of study medication will be given
- **treatment phase:** starting from the first dose of study medication administration until the morning of day 4 or earlier in case of successful decongestion prior to day 4.
- **follow-up phase:** starting when the treatment phase ends until 3 months after the study start dose.

[figure not shown]

Figure 1. Trial Flow Chart

4.1 Study objectives and endpoints

4.1.1 Rationale

Guidelines from international cardiac societies lack high-quality data on the optimal dosing, timing and method of delivery of diuretic agents. In the Diuretic Optimization Strategies Evaluation (DOSE) trial¹, which is the only randomized clinical trial on diuretic therapy for decompensated HF patients, no differences in patients' global assessment of symptoms or change in renal function were observed when loop diuretics were administered by bolus as compared with continuous infusion or at high versus low dose during a hospitalization for decompensated HF. Of note, only a minority of patients (15%) were adequately decongested after 72 h in the DOSE trial, Acetazolamide is a largely forgotten diuretic, but can potentially boost diuretic response. Acetazolamide targets the proximal tubule of the kidney, where the majority of sodium is reabsorbed. The ADVOR trial will examine if an improved application of existing decongestive therapies by adding acetazolamide, will result in a better outcome for patients and society.

4.1.2 Primary Objective and outcome measure

Primary Objective	Primary Endpoint
To investigate if combination therapy with acetazolamide improves loop diuretic efficacy to increase diuresis in decompensated HF patients with volume overload, allowing for a better/faster decongestion and a lower total dose of loop diuretics.	The proportion of patients achieving decongestion on the morning of day 4 without the need for escalating therapy on the morning of day 3 (treatment success).

Definition of primary endpoint

Congestion is assessed using the **volume assessment score** (also called the congestion score see figure 2). Freedom from volume-overload will be defined as not more than trace oedema, no residual pleural effusion, and no residual ascites (Figure 2).

So a (sum) score ≤ 1 indicates that decongestion is achieved (being dry), a score > 1 is considered to be volume overloaded (decongestion not achieved).

The primary endpoint is a binary endpoint, with a success defined in case of:

- decongestion (volume assessment score ≤ 1) on the morning of day 2
- or decongestion (volume assessment score ≤ 1) on the morning of day 3
- or decongestion (volume assessment score ≤ 1) on the morning of day 4 **without** the need for escalating diuretic strategy on the morning of day 3, which is needed if total urinary output on the morning of day 3 $< 3.5l$ (sum of urinary output from the start of IMP until the morning of day 3).

[figure not shown]

Figure 2. Clinical Congestion Assessment

The SOC therapy results in ~15% effective decongestion¹. It is estimated that the combination therapy should have a success rate of 25%, which represents a clear meaningful absolute benefit of 10% more patients with appropriate decongestion after 72h.

4.1.3 Secondary objectives and endpoints

Secondary Objectives	Secondary Endpoints

To investigate if combination therapy with acetazolamide:
 
 - leads to improved clinical outcome in decompensated HF (less HF readmissions, lower all-cause mortality) - shortens the length of stay in patients with decompensated HF, which is expected to reduce health care expenditure - leads to improved quality of life 	
 - Combined endpoint of all-cause mortality and HF readmission during 3 months of follow-up - Length of index hospital admission - Change in EuroQoL

Definition of secondary endpoints

- The combined endpoint of all-cause mortality and HF readmission during 3 months of follow-up is a binary endpoint. The time to the combined endpoint will be calculated as the time between start of study medication (day 1) and the date of (first) HF readmission or mortality (whichever comes first). *HF readmission* is defined as either a hospital admission or an unscheduled contact at the emergency department and when

treatment with intravenous loop diuretics is initiated because of worsening HF.

- Length of index hospital admission (calculated in days) is obtained as the date of discharge from the hospital minus the date of screening +1.
- EuroQol is a five dimension patient-reported QoL questionnaire (EQ-5D-5L). The EQ-5D-5L health states, defined by the EQ-5D-5L descriptive system, are converted into a single index value (<https://kce.fgov.be/nl/een-belgische-waardenset-voor-de-eq-5d-5l-%E2%80%93-hoe-gezondheidsgerelateerde-levenskwaliteit-waarderen>). The VAS assessment of the EQ-5D will also be used. The EQ VAS records the patient's self-rated health on a vertical visual analogue scale.

The index values and EQ-VAS at baseline, the morning of day 4 or discharge (whatever comes first), and at 3 months of follow-up will be used for the secondary objective.

During the study the baseline EQ-5D-5L questionnaire has been completed as soon as possible after screening up to day 1.

4.1.4 Safety objectives and endpoints

Safety Objective	Safety Endpoints
To evaluate the safety of the combination therapy with acetazolamide in this patient population.	
 - Severe metabolic acidosis at any time during study treatment - Doubling or more ($\geq 2x$) of baseline serum Creatinine, or $\geq 50\%$ decrease in baseline eGFR at any time during study treatment - Hypokalaemia at any time during study treatment - Hypotension at any time during study treatment

Definition of Safety endpoints

- Severe metabolic acidosis: a value of bicarbonate < 12 mmol/L at any time during study treatment (day 1- day 4)
- Worsening of eGFR or the need for renal replacement therapy during the index hospitalization. eGFR is obtained via the CKD-EPI formula. The eGFR values will be calculated (in mL/min/1.73 m²) from the local laboratory creatinine measurements using the CKD-EPI formula (Levey et al 2009)².
- Hypokalaemia: a value of potassium $\leq 3,0$ mmol/L at any time during study treatment (day 1- day 4)
- Hypotension: a value of systolic blood pressure < 85 mmHg at any time during study treatment (day 1- day 4)

Baseline laboratory value

For all laboratory variables, the baseline value is defined as the last value prior to the first dose of study drug.

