7.7 Treatment phase assessments

7.7.1 Day 1

- Request patient to empty their bladder before administration of the first dose of loop diuretics.
- Administer the first bolus of loop diuretics and acetazolamide or placebo to the patient.
- Start the urinary collection immediately after first bolus of loop diuretics and acetazolamide or placebo is administered. The collection will stop the latest as close to but prior to the morning bolus of study medication on day 3. Urinary catheter insertion is strongly recommended but not mandatory to achieve an optimal urine collection. However, in case of urinary incontinence, placement of a urinary catheter is mandatory. Care should be taken to ensure ALL urine is collected. For more details regarding the study urinary collection see [appendix 4](#).

If the patient is enrolled between midnight and 6 a.m., day 1 assessments and day 2 assessment can be performed on the same day but only if there is a difference of minimum 6 hours between the start of the study medication on day 1 and study medication on day 2.

7.7.2 Day 2, Day 3 and Day 4

- Collect vital signs including body weight, arterial blood pressure, heart rate
- As long as patient is assessed as volume overloaded during the previous volume assessment, perform volume assessment by the Principal Investigator or a Sub-investigator who has been trained in the study volume assessment (Figure 3 in section 8)
- Collect morning blood sample for local laboratory assessment: serum haemoglobin, haematocrit, electrolytes (Na, K, Cl, HCO₃), serum urea, serum Cr, serum albumin.
- On the morning of Day 2 and Day 3, collect an urine sample from urine collection period 1 and period 2 respectively for analysis in local lab. In case patient is participating in the optional laboratory sub-study, collect an additional urine sample for each urine collection period for shipment to the University Biobank Limburg for storage and additional research (see [section 7.10](#)). Urinary collection will stop at the morning of day 3 ([appendix 4](#)).
- In case patient is still volume overloaded continue study treatment as described in [section 8](#)
- Collect concomitant medication ([see Appendix 5](#))
- Document and assess adverse events ([section 9](#))
- In addition, on the morning of day 4 or at discharge (whatever comes first):
 - EQ-5D to be completed by the patient.

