4.1.5 Exploratory objectives and endpoints

Exploratory Objectives	Exploratory endpoints
To determine whether acetazolamide compared with placebo in combination with loop diuretics will have an effect on body weight.	Change in body weight.
To determine whether acetazolamide compared with placebo in combination with loop diuretics will reduce the incidence of all cause rehospitalisation's.	All cause rehospitalisation during first 3 months after study start dose.
To determine whether acetazolamide compared with placebo in combination with loop diuretics will have an effect on total urinary volume and natriuresis.	Total urinary volume and natriuresis starting from first intravenous (IV) diuretic administration at randomization until the morning of day 3.
To determine whether acetazolamide compared with placebo in combination with loop diuretics will have an effect on plasma natriuretic peptides.	Change in plasma natriuretic peptides change from screening until day 4 or at discharge (whatever comes first) and at 3 months follow up visit.
To determine whether acetazolamide compared with placebo in combination with loop diuretics will have an effect on the total dose of IV loop diuretics used during first 4 days.	Total dose of IV loop diuretics used during first 4 days.
Effect of decongestion on uptitration of neurohormonal blockers	Changes in doses of neurohumoral blockers.
To determine whether acetazolamide compared with placebo in combination with loop diuretics will reduce the need for renal replacement therapy.	Need for renal replacement therapy or ultrafiltration during first 3 months after study start dose.
To determine whether acetazolamide compared with placebo in combination with loop diuretics will reduce the incidence of hyponatremia during treatment phase.	Hyponatremia during treatment phase.
To evaluate if liver dysfunction at screening has an effect on the treatment effect on the primary endpoint.	Liver dysfunction at screening and primary endpoint.
To determine whether acetazolamide compared with placebo in combination with loop diuretics will have an effect on plasma volume changes during treatment phase.	Change in plasma volume during treatment phase (assessed by albumin and hematocrit)

Exploratory Objectives	Exploratory endpoints
To evaluate if iron deficiency at screening has an effect on the treatment effect on the primary endpoint	Iron deficiency at screening and primary endpoint

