5.12 Analysis of safety outcomes

For the safety endpoints, all patients that were randomized and received at least 1 dose of the investigated drug or placebo will be included. For the safety analysis, patients will be grouped based on the actual study treatment received.

The safety outcomes are all binary outcomes. For descriptive purposes, the number (%) of failure and success for each safety outcome will be given per treatment arm.

For each safety outcome, the treatment effect will be evaluated by means of a generalized linear mixed model (logistic model). The statistical model will include a fixed treatment effect, and a random centre effect. The results of this model will be presented as an odds-ratio (OR), 95% confidence interval and the associated p value.

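### The hypokalaemia and severe-acidosis safety endpoints have no new-onset condition and no baseline adjustment, so low values that persist from before dosing count as events and attenuate the odds ratio.

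*Combined protocol and SAP*

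**What the plan says.** SAP v2.0, section 4.1.4, lists four safety endpoints. Two use a fixed laboratory limit: bicarbonate below 12 mmol/L for severe metabolic acidosis, and potassium of 3.0 mmol/L or lower for hypokalaemia. Each is met by one value, in "mmol/L at any time during study treatment (day 1- day 4". Neither has a condition on the starting value.

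The other two are protected. The renal endpoint is relative to the patient's own start (a doubling of creatinine, or a 50% "decrease in baseline eGFR at any time during study treatment"). Hypotension is a systolic pressure below 85 mmHg, and section 4.2.2 excludes patients below 90 mmHg at screening. Sections 4.2.1 and 4.2.2 set no limit on potassium or bicarbonate.

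Section 4.1.4 also supplies a baseline: "For all laboratory variables, the baseline value is defined as the last value prior to the first dose of study drug". Section 5.12 does not use it. It takes every randomised patient who received a dose, and of its logistic mixed model it says: "The statistical model will include a fixed treatment effect, and a random centre effect".

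On sampling, protocol v2.0 section 7.6 takes electrolytes, including bicarbonate, at screening before the study diuretics. Section 7.7.2 then instructs, for days 2, 3 and 4: "Collect morning blood sample for local laboratory assessment". Section 7.7.1 lists no laboratory sample for day 1.

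**The concern.** A fixed-limit endpoint without a baseline condition mixes two groups: patients who cross the limit after dosing, and patients who were beyond it beforehand and have not recovered. The second group adds similar numbers of events to both arms and carries less information about what the drug causes, so the odds ratio moves towards 1. For a harm endpoint, that is the wrong direction in which to err.

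Such patients are plausible here. Everyone has taken an oral loop diuretic for at least a month, thiazides are stopped only at inclusion, and up to 2 mg of intravenous bumetanide is allowed before randomisation.

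The trial has no data safety monitoring committee and no interim analysis. The Trial Steering Committee reviews safety data periodically, but the comparison in SAP 5.12 is the planned between-arm test for these two harms.

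The window label adds an ambiguity. SAP 4.1.3 equates day 1 with the start of study medication, while the pregnancy-test text in protocol 9.2 attaches Day 1 to the screening phase. A programmer could therefore read a pre-dose sample taken on that date into the day 1 to day 4 window.

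**Working it through.** **The plan's own figure.** The documents state no event rate, baseline prevalence or power for any safety endpoint. The only figure to reproduce is the sample size in SAP 4.5, which supplies the arm size. For 15% versus 25%, two-sided 5%, 80% power, unpooled variance:

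(1.960 + 0.842)² × (0.15 × 0.85 + 0.25 × 0.75) / 0.10² = 247.2 per arm, 494.5 in total, against the stated 494. Then 494 × 1.05 = 518.7, the stated 519. I use 259 per arm.

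**Model for the dilution.** Let *b* be the share beyond the limit before dosing, *q* the share of those with a post-dose value still beyond it (taken as equal in both arms), and *p* the new-onset rate among the rest. The rate counted under SAP 4.1.4 is

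counted rate = (1 − *b*) × *p* + *b* × *q*.

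**Inputs.** All are assumptions: *p* = 3% on placebo and 8% on acetazolamide, *b* = 2% or 4%, *q* = 100% or 50%. The new-onset odds ratio is (0.08/0.92) / (0.03/0.97) = 2.81.

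Worked case, *b* = 2%, *q* = 100%:
- placebo: 0.98 × 0.03 + 0.02 = 0.0494
- acetazolamide: 0.98 × 0.08 + 0.02 = 0.0984
- odds ratio: (0.0984/0.9016) / (0.0494/0.9506) = 2.10

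Power below is for a Wald test of the log odds ratio at 259 per arm.

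| *b* | *q* | placebo | acetazolamide | odds ratio | risk difference (points) | power |
|---|---|---|---|---|---|---|
| 0 | – | 3.00% | 8.00% | 2.81 | 5.0 | 67% |
| 2% | 50% | 3.94% | 8.84% | 2.36 | 4.9 | 60% |
| 2% | 100% | 4.94% | 9.84% | 2.10 | 4.9 | 55% |
| 4% | 50% | 4.88% | 9.68% | 2.09 | 4.8 | 54% |
| 4% | 100% | 6.88% | 11.68% | 1.79 | 4.8 | 46% |

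The risk difference shrinks only by the factor (1 − *b*). Counting new onset only, with the 4% removed (259 × 0.96 = 249 per arm), keeps the odds ratio at 2.81 with power of about 65%.

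**Low prevalence.** At *b* = 1% the same rates give 2.37 to 2.56. With new-onset rates of 5.0% and 9.5% (odds ratio 2.00), *b* = 1% gives 1.84 to 1.91 and *b* = 0.5% gives 1.91 to 1.95. What matters is *b* × *q* relative to the new-onset rate, so low prevalence makes the loss small only where new events are clearly more common than persistent ones.

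**The case against.** **Tempting broader readings that the documents do not support.** A reader might infer that all the laboratory safety endpoints ignore baseline. They do not: creatinine/eGFR is defined against it. A reader might add hyponatraemia, but SAP 4.1.5 says only "hyponatremia during treatment phase", with no sodium limit and no day-1 window. That is an undefined endpoint, a different matter.

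**A low value before dosing is not in itself an event.** The endpoints are worded as on-treatment, pre-dose values are baseline by definition, and Appendix A stores the screening laboratory values as separate D0 variables. This stands: the patient counts only if a later value is also beyond the limit, or if the window is misread. Nor is every day-1 sample necessarily pre-dose. Protocol 7.7.1 lets patients enrolled between midnight and 6 a.m. have day 1 and day 2 assessments on the same date.

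**Persistence may be well under 100%.** SAP 4.3.3 provides for potassium below 4 mmol/L and bicarbonate below 20 mmol/L to be treated. This also stands, and is why the table includes 50%.

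**Randomisation balances prevalent cases in expectation, and section 5.12 reports counts and percentages per arm.** Correct. Chance imbalance is already in the standard error, and the risk difference hardly changes. The claim that harm would be hidden goes too far; what is attenuated is the odds ratio and its test.

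**Any value versus new onset is a choice of estimand, and SAP 5.3 calls every non-primary endpoint exploratory.** Fair. Restricting the analysis to patients normal at baseline drops those who start closest to harm. That argues for keeping everyone and adjusting, and against a large claim about severity. It does not explain why a defined baseline goes unused.

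**Conclusion.** The point holds for potassium and bicarbonate only. As written, a low value that persists from before dosing counts as a treatment-phase event, and nothing in the entry criteria or the model offsets this. The odds ratio is attenuated and the risk difference almost unchanged.

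Under the assumed new-onset rates of 3% and 8%, an odds ratio of 2.81 becomes 2.10 to 2.36 at 2% baseline prevalence and 1.79 to 2.09 at 4%, for persistence of 100% down to 50%. It is a smaller matter at 1% or less, which may be the case for bicarbonate below 12. Every rate is assumed, and the calculation takes persistence to be the same in both arms. The documents support the direction of the effect but not any particular size. This is a cheap improvement to two exploratory safety comparisons and does not bear on the primary result.

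**What to change.** - **SAP 4.1.4:** state that only samples taken after the first dose count towards hypokalaemia and severe metabolic acidosis.
- **SAP 5.12:** add the baseline potassium value to the hypokalaemia model and the baseline bicarbonate value to the acidosis model, using the baseline already defined in 4.1.4. All dosed patients stay in.
- **Reporting:** give per arm the number already beyond each limit at baseline, with new-onset counts as a supportive summary. Appendix A lists baseline potassium but not bicarbonate, so add it.

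The cost is SAP wording and one covariate per model; both values are collected at screening under protocol 7.6. The adjusted odds ratio is conditional on baseline and should be labelled so. If acidosis events are very few the adjusted model may be unstable; in that case report only the new-onset counts for that endpoint.

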Non-cardiovascular death: any death that is not thought to be due to a cardiovascular cause

- Rehospitalisation for heart failure is defined as either a hospital admission or an unscheduled contact at the emergency department for worsening HF if the patient is treated with intravenous loop diuretics.
- Need for Renal replacement therapy: ultrafiltration or dialysis

The site will need to submit a complete endpoint package within 30 days upon request of the sponsor to [contact]. This package should include anonymized source documents (SDs) relevant to the endpoint reported (e.g. discharge letter, emergency room notes, etc). The SD should include at least the reason for admission/death and the received treatment for the event (if applicable). The original SDs need to be retained at the site.

Identifying a pregnancy

All pre- menopausal women who are not surgically sterile will have pregnancy urine tests performed at screening phase (Day 1). A positive pregnancy test at day 1 constitutes in a screening failure.

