4.3.2 Treatment DOSE ADJUSTMENTS in case of an inappropriate diuretic response

If the total urinary output on the morning of day 3 is < 3500 mL and the patient is still volume overloaded, an escalation of decongestive treatment is mandatory. One of the outlined three options can be chosen at the discretion of the treating physician.

Escalation therapy options:

- doubling of the IV dose of the loop diuretics
- add oral chlorthalidone 50 mg once daily
- ultrafiltration or renal replacement therapy might be considered

The decision to proceed with escalation therapy will be collected in the case report as the need for escalation implies a failure for the primary endpoint.

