5.10 Analysis of the primary outcome

5.10.1 Main analysis

The primary statistical analysis in ADVOR will be an intention-to-treat (see section 5.5).

The primary endpoint is a binary outcome with a success defined as decongestion achieved on the morning of day 4 (or earlier) without the need for escalating diuretic strategy (doubling loop diuretic dose, addition of chlorthalidone, or ultrafiltration) during IV diuretic therapy on morning of day 3.

For descriptive purposes, the number (%) of failure and success for the primary outcome will be given per treatment arm.

The treatment effect for this primary outcome will be evaluated by means of a generalized linear mixed model (logistic model⁶⁷). The statistical model will include a fixed treatment effect, and a random centre effect. The results of this model will be presented as an odds-ratio (OR), 95% confidence interval and the associated p value.

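### SAP 4.1.4 defines the renal safety endpoint in two conflicting ways, and one of them can count ultrafiltration given for congestion as kidney harm

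*Combined protocol and SAP*

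**What the plan says.** **Renal safety endpoint (SAP v2.0, 4.1.4).** The table row is purely laboratory: serum creatinine at least twice baseline, or a 50% or greater "decrease in baseline eGFR at any time during study treatment". The list of definitions under the table describes the same endpoint as "Worsening of eGFR or the need for renal replacement therapy during the index hospitalization". It names the CKD-EPI formula but gives no size of eGFR fall.

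**Renal replacement (protocol v2.0, 9.2).** The endpoint event sent for adjudication reads "Need for Renal replacement therapy: ultrafiltration or dialysis". The SAP has no definition of its own.

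**Day-3 escalation (SAP 4.3.2; the same rule is in protocol 8.1).** Escalation is mandatory "If the total urinary output on the morning of day 3 is < 3500 mL and the patient is still volume overloaded". One of the three options reads "ultrafiltration or renal replacement therapy might be considered". For any escalated patient, "the need for escalation implies a failure for the primary endpoint". The main analysis (SAP 5.10.1) lists the escalating strategies as "doubling loop diuretic dose, addition of chlorthalidone, or ultrafiltration".

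**Exploratory endpoint (SAP 4.1.5).** "Need for renal replacement therapy or ultrafiltration during first 3 months after study start dose", which matches tertiary endpoint 9 in protocol 3.6.

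**Handling.** SAP 4.4 sends renal replacement events to the Endpoint Adjudication Committee (EAC). SAP 5.12 plans one logistic mixed model per safety outcome.

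**The concern.** The two statements in 4.1.4 differ in content, threshold and time window, so the event to be modelled is not fixed. For the other three safety endpoints (acidosis, hypokalaemia, hypotension) the table only names the event and the list supplies the cut-off. An analyst could therefore reasonably take the list as operative for the renal endpoint too.

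On that reading, and with the protocol's definition of renal replacement, ultrafiltration chosen on day 3 for residual congestion becomes a kidney-harm event. The trigger is urine volume plus volume overload; creatinine and eGFR play no part. One clinical decision then counts against efficacy and against renal safety.

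The direction matters. Secondary objective 2 in protocol 3.2 expects less escalation on acetazolamide. If that is right, escalation by ultrafiltration adds more renal events on placebo than on acetazolamide and offsets any true renal harm from the drug. There is no data safety monitoring committee and no interim analysis, so the final comparison carries much of the comparative renal evidence.

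**Working it through.** **1. The plan's own figure.** No figure is given for the renal endpoint. The only sizing is for the primary endpoint: 15% versus 25%, two-sided 5%, power 80%. Unpooled formula: (1.960 + 0.842)² × (0.15×0.85 + 0.25×0.75) / 0.10² = 7.849 × 0.315 / 0.01 = 247.2 per arm. That is 494 if truncated and 496 if rounded up; the pooled version gives 500. Then 494 × 1.05 = 518.7, so 519, or about 259 per arm. The sizing reproduces and is not in question.

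**2. The two statements side by side.**

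| | Table row | Definition list |
|---|---|---|
| Laboratory criterion | creatinine ≥2× or eGFR fall ≥50% | eGFR worsening, no threshold |
| Renal replacement | not included | included |
| Window | study treatment | index hospitalization |
| Day-3 ultrafiltration for congestion, stable kidneys | no event | event, if protocol 9.2 applies |

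**3. Effect of counting it.** Let k be the true kidney-event rate, e the escalation rate and u the share of escalations done by ultrafiltration. Taking ultrafiltration as independent of true kidney events, the counted rate is k + (1 − k) × e × u.

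The documents give none of these rates; all values here are assumptions. The only bound available is that escalated patients are failures, so under the planned success rates escalation cannot exceed 85% versus 75%.

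Take k = 2% placebo, 5% acetazolamide, and e = 40% versus 30%. At u = 5%:
- placebo: 0.02 + 0.98 × 0.40 × 0.05 = 3.96%
- acetazolamide: 0.05 + 0.95 × 0.30 × 0.05 = 6.42%
- odds ratio 1.67

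| u | Placebo | Acetazolamide | Odds ratio | Power, 259 per arm |
|---|---|---|---|---|
| 0 | 2.00% | 5.00% | 2.58 | 46% |
| 1% | 2.39% | 5.29% | 2.28 | 40% |
| 5% | 3.96% | 6.42% | 1.67 | 24% |
| 10% | 5.92% | 7.85% | 1.35 | 14% |
| 20% | 9.84% | 10.70% | 1.10 | 5% |
| 33% | 15.07% | 14.50% | 0.96 | sign reversed |

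**4. Range over escalation rates.** With 20% versus 15% the odds ratio is 1.97 at u = 5%, 1.67 at 10% and 1.16 at 33%. With 85% versus 75% it is 1.43, 1.20 and 0.95.

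The risk difference is zero at u = (k₁ − k₀) / [(1 − k₀)e₀ − (1 − k₁)e₁], with 0 for placebo and 1 for acetazolamide. For 40% versus 30% this is 0.03 / (0.392 − 0.285) = 28%. It is 56% for 20% versus 15%, and 25% for 85% versus 75%. With kidney events of 1% versus 3% the corresponding points are about 19%, 38% and 18%.

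**5. No difference in escalation.** With 30% escalating in both arms the odds ratio is 1.91 at u = 5% and 1.27 at 33%. The effect is diluted but not reversed.

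**The case against.** **The table row is laboratory-only.** Under it no ultrafiltration patient counts and the overlap disappears. This stands, and it is why the point is conditional. A reader might infer that the plan settles the matter and does count ultrafiltration as renal harm; the documents do not support that, because section 4.1.4 contradicts itself.

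**The SAP names ultrafiltration separately from renal replacement** in 4.1.5, 4.2.2 and 4.3.2, whereas 4.1.4 mentions only renal replacement. This stands as evidence of ambiguity. It does not remove the overlap: protocol 9.2 merges the two, and 4.3.2 offers renal replacement itself under the same non-renal trigger.

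**The EAC reviews these events.** It does, but no document gives it a rule by indication, and under protocol 9.2 ultrafiltration for congestion qualifies as written.

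**The effect may be trivial.** Ultrafiltration is worded more tentatively than the other two options, and patients escalated by doubled loop diuretic or chlorthalidone are not double-counted. Even uncontaminated, kidney events of 1% versus 2% would give only about 15% power. All of this stands.

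**Other views of kidney harm exist.** Worsening renal function is tertiary endpoint 13 in protocol 3.6, and serious adverse events are collected. This softens the consequence, though the SAP's exploratory table does not carry endpoint 13 forward.

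**The exploratory endpoint has the same flaw.** A reader might infer this too. It does not follow: that endpoint openly names both procedures and measures their use, as the protocol declares.

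**Conclusion.** The renal safety endpoint has two incompatible definitions. One of them, read with protocol 9.2, lets a treatment for congestion count as kidney harm. The bias would favour acetazolamide if the drug lowers escalation, and would only dilute if it does not.

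The size cannot be stated from the documents. It depends on the escalation rates, the ultrafiltration share and the kidney-event rates, and it is nil if neither ultrafiltration nor renal replacement is used to escalate.

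A reader might go further and infer that a doubling of kidney harm would all but vanish. With kidney events of 1% versus 2% (2.6 versus 5.2 patients), escalation of 40% versus 25% and a 5% share, the added counts are 259.5 × 0.40 × 0.05 = 5.2 and 259.5 × 0.25 × 0.05 = 3.2. The ratio becomes (5.2 + 3.2) / (2.6 + 5.2) = 1.08. But the same sum gives about 1.25 at a 3% share, 1.6 at 1% and 2 at zero. Masking is a possibility that the plan leaves open, not a result it implies.

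**What to change.** Before unblinding:

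- Reconcile the table row and definition list in SAP 4.1.4 into one endpoint with one content, one eGFR or creatinine threshold and one window, consistent with protocol 9.2 and SAP 4.3.2.
- State that ultrafiltration or renal replacement given as day-3 escalation for congestion is not a kidney-harm event. Take the indication from the source packages the EAC already receives. The required minimum content of these packages does not name the indication for a procedure, so cross-check against the escalation decision recorded in the case report form.
- Report the creatinine/eGFR criterion, dialysis and ultrafiltration separately by arm beside the model in SAP 5.12.
- Leave the exploratory endpoint in SAP 4.1.5 as declared, but tabulate ultrafiltration and dialysis separately.

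The cost is SAP wording, a blinded judgement of indication, and possibly a second look at cases already adjudicated, since the SAP reports that the trial has been completed. The component table needs no new judgement and would by itself expose any masking. No change to patient management is proposed, and no view is taken on which escalation option should be used.
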